6.4.2. Disease Status Follow-Up

Subjects who discontinue study treatment for a reason **other than** disease progression (eg, toxicity) will move into the disease status follow-up period and should be assessed every 8 weeks (\pm 7 days), for 12 months. After 12 months, radiologic assessments will be performed every 12 weeks until disease progression is determined. Every effort should be made to collect information regarding disease status until:

- The start of new antineoplastic therapy.
- Disease progression.
- Death.
- The end of the study.
- Withdrawal of consent.

Note: As of Protocol Amendment 5, disease status follow-up will no longer be required beyond the last safety follow-up visit for subjects who discontinue study treatment for a reason other than disease progression. The last disease status follow-up data will be recorded in the eCRF at the time of the last safety follow-up visit. The last study visit will be the last safety follow-up visit.

6.4.3. Survival Follow-Up

Once a subject has received the last dose of study treatment, confirmed disease progression, or starts a new anticancer therapy, the subject moves into the survival follow-up period and should be contacted by telephone, email, or visit at least every 12 weeks (+ 7 days) to assess for survival status until death, withdrawal of consent, or the end of the study, whichever occurs first.

Note: As of Protocol Amendment 5, survival follow-up will no longer be required beyond the last safety follow-up visit for subjects who have confirmed disease progression or start a new anticancer therapy. The last survival follow-up data will be recorded in the eCRF at the time of the last safety follow-up visit. The last study visit will be the last safety follow-up visit.

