4.4. Duration of Treatment and Subject Participation

After signing the ICF, screening assessments may be completed over a period of up to 28 days. Subjects may continue to receive study treatment as long as they are deriving benefit and have not met any of the Protocol-defined conditions for treatment withdrawal (see Section 5.5), or for

up to 24 months from the first dose of study treatment, whichever occurs first. If the subject discontinues study treatment, the treatment period will end and the subject will enter the follow-up period (see Section 6.4). Study participation, including post-treatment follow-up is expected to average approximately 12 to 18 months per individual subject.

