5.5.2. Withdrawal Procedures

In the event that the decision is made to permanently discontinue the study treatment, the subject will be withdrawn, and the EOT visit should be conducted. Reasonable efforts should be made to have the subject return for all applicable follow-up visits (safety and efficacy; see Section 6.4). The last date of the last dose of study treatment and the reason for subject withdrawal will be recorded in the eCRF.

If a subject is withdrawn from the study treatment:

- The study monitor or sponsor must be notified.
- The reason(s) for withdrawal from treatment must be documented in the subject's medical record and in the eCRF.

Note: The reason for withdrawal from treatment may be different than the reason for withdrawal from study. For example, subjects can discontinue treatment for disease progression or toxicity, but remain in the study for safety and survival follow-up.

Note: As of Protocol Amendment 5, subjects who discontinue treatment will no longer be followed for progression and survival beyond the last safety follow-up visit.

- The EOT visit should be performed.
- The date of the EOT visit should be recorded in the eCRF and IRT.
- Subjects must be followed for safety until the time of the follow-up visit or until study treatment-related toxicities resolve, return to baseline, or are deemed irreversible, or until the subject begins new anticancer therapy, whichever is longest.
- Subjects who discontinue for reasons other than disease progression will continue to be followed for disease status as outlined in Section 6.4.2.

Note: As of Protocol Amendment 5, subjects who discontinue for reasons other than disease progression will no longer be followed for disease status beyond the last safety follow-up visit.

- All subjects who discontinue study treatment will continue to be followed for OS as outlined in Section 6.4.3.

Note: As of Protocol Amendment 5, subjects who discontinue study treatment will no longer be followed for survival beyond the last safety follow-up visit.

If the subject discontinues study treatment and actively withdraws consent for collection of follow-up data (safety follow-up, disease assessments, or survival follow-up), then no additional data collection should occur; however, **subjects will have the option of withdrawing consent for study treatment but continuing in the follow-up period of the study for safety, efficacy, and survival assessments.**

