6.4. Follow-Up

6.4.1. Safety Follow-Up

The safety follow-up period is the interval between the EOT visit and the scheduled follow-up visit, which should occur 30 days (+ 7 days) and 60 days (+ 7 days) after the last dose of study treatment. Monitoring for the occurrence of new AEs should be continued for at least 60 days after the last dose of study treatment or until the start of new anticancer therapy, whichever occurs first. Reasonable efforts should be made to have the subject return for the follow-up visits and report any AEs that may occur during this period. If a subject is scheduled to begin a new anticancer therapy before the end of the 30-day or 60-day safety follow-up period, the safety follow-up visit should be performed before new anticancer therapy is started. Once new anticancer therapy has been initiated, AEs and SAEs will no longer be collected, and the subject will move into the survival follow-up period.

Note: As of Protocol Amendment 5, the safety follow-up visits will include AE and concomitant medication assessment only and may be completed remotely (such as by televisit).

Note: As of Protocol Amendment 5, if a new anticancer therapy has been initiated before the end of the safety follow-up period, no further survival follow-up assessment will be required beyond the last safety follow-up visit.

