APPENDIX C. PROTOCOL AMENDMENT SUMMARY OF CHANGES

DOCUMENT HISTORY	
Document	Date
Amendment (Version) 1:	12 JUN 2017
Amendment (Version) 2:	22 AUG 2017
Amendment (Version) 3:	18 DEC 2017
Amendment (Version) 4:	24 OCT 2018
Amendment (Version) 5:	22 JAN 2021

Amendment 5 (22 JAN 2021)

Overall Rationale for the Amendment:

The primary purpose of this amendment is to provide guidance for the management of ongoing subjects, as enrollment is complete and sufficient data have been collected for primary and secondary endpoint analysis.

1. **Synopsis; Section 5.5.1, Withdrawal Criteria; Section 5.5.2, Withdrawal Procedures; Section 6, Study Assessments (Table 10: Schedule of Clinical Assessments); Section 6.3, End of Treatment; Section 6.4.1, Safety Follow-Up; Section 6.4.2, Disease Status Follow-Up; Section 6.4.3, Survival Follow-Up; Section 7.5, Poststudy Anticancer Therapy Status; Section 7.7.1.1.3, Imaging During Follow-Up; Section 7.11.2, Data Collection for Survival Follow-Up**

Description of change: Disease status and survival follow-up data will only be collected until the last safety follow-up visit. Safety follow-up visits will only include AE and concomitant medication assessments.

Rationale for change: To update the study assessments as enrollment is complete and all ongoing subjects have either been on study treatment for more than 15 months or are in follow-up after treatment discontinuation (for any of the treatment withdrawal criteria outlined in Section 5.5).

2. **Section 10.1.1, Identification of the Coordinating Principal Investigator; Section 10.6, Publication Policy; Section 10.7, Study and Site Closure**

Description of change: Included the process for identification of the coordinating principal investigator and for study and site closure. Clarified the policy for study publications.

Rationale for change: To update applicable sections as per current protocol template.

3. **Incorporation of administrative changes:** Other minor administrative changes have been incorporated throughout the Protocol to correct inadvertent inconsistencies or improve the readability and are noted in the redline version of the amendment.

Amendment 4 (24 OCT 2018)

Overall Rationale for the Amendment:

The primary purpose of this amendment is (1) to introduce [REDACTED] and (2) to explore the combination therapy of INCAGN01876 with nivolumab in subjects with PD-1 refractory SCCHN.

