### 7.3.8. Overall Survival

Overall survival is defined as the interval between Cycle 1 Day 1 and the date of death due to any cause. Date of death will be determined using the Death Report, the Survival Follow-Up, and the Subject Status CRFs. Subjects who are lost-to-follow-up or still alive at the time of analysis will be right-censored at the earlier of the date the subject was last known alive and the clinical data cutoff date for the analysis. The last known alive date is defined as the later of the last study visit and the date the subject was last known alive from the Survival Follow-Up and Subject Status CRFs.

Kaplan-Meier time to event curves will be presented by treatment groups. Median survival will be estimated using the KM method. Kaplan-Meier estimates of 1-year and 2-year survival probabilities will be provided. Confidence intervals for median survival time will be calculated using the method of Brookmeyer and Crowley (1982).

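### After Amendment 5, survival follow-up depends on treatment status for subjects under 24 months from first dose, so 2-year OS can be biased upward unless SAP 7.3.8 fixes one common cutoff

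*Protocol*

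**What the plan says.** **Before Amendment 5.** Protocol 6.4.3 required contact "at least every 12 weeks (+ 7 days) to assess for survival status until death, withdrawal of consent, or the end of the study". This applied to subjects off treatment, whatever their outcome.

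**From Amendment 5.** The note in 6.4.3 says that "survival follow-up will no longer be required beyond the last safety follow-up visit" for subjects with confirmed progression or a new anticancer therapy. Protocol 5.5.2 extends it to everyone who stops: "subjects who discontinue study treatment will no longer be followed for survival beyond the last safety follow-up visit". The synopsis and sections 6.3 and 7.11.2 agree. The last safety visit falls "60 days (+ 7 days) after the last dose of study treatment" (6.4.1). Treatment may continue for "up to 24 months from the first dose of study treatment, whichever occurs first" (4.4).

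**Reason given.** Appendix C says enrolment is complete and "sufficient data have been collected for primary and secondary endpoint analysis". It adds that ongoing subjects had either been treated for more than 15 months or were in follow-up after stopping. It gives no OS counts or enrolment dates.

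**Analysis.** One-year and 2-year OS is a secondary objective. SAP 7.3.8 estimates both by Kaplan-Meier. Subjects alive or lost to follow-up "will be right-censored at the earlier of the date the subject was last known alive and the clinical data cutoff date" for the analysis, and that date is not specified. The SAP is based on Protocol Amendment 2 (SAP 2.1). Its only listed version is dated 05 DEC 2017 (SAP Table 14), about three years before the follow-up rule changed.

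**The concern.** Kaplan-Meier needs subjects censored at a given time to have the same later prognosis as those still at risk. Take two subjects, both 18 months from first dose when Amendment 5 takes effect. One stopped treatment months ago and has completed the safety visits, so is censored at about month 18. The other is still on treatment and stays under observation, possibly to month 24 and the safety visits after it. If the second subject stops for progression at month 20, observation ends near month 22, before much of the post-progression mortality can be seen.

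Between months 15 and 24 the later-enrolled subjects therefore stay in the risk set mainly while they are on treatment or have just stopped. If death is slower on treatment than after it, the pooled late hazard is too low and 2-year OS too high. At stake is a secondary efficacy estimate that readers would compare with historical survival.

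**Working it through.** The documents give no OS rate, event count or enrolment curve, so there is no stated figure to reproduce. The check has two parts.

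**1. Who is exposed (dates from Appendix C)**
- 22 JAN 2021 minus 24 months is 22 JAN 2019. Anyone first dosed before then had 24 months of potential survival contact under the earlier rule. Only later entrants are exposed for 2-year OS.
- Amendment 3 (18 DEC 2017) already reports Phase 1 responses. It precedes Amendment 5 by 1,131 days, or 1,131 / 30.44 = 37.2 months. Those subjects are not exposed.
- Amendment 4 (24 OCT 2018) added the PD-1 refractory SCCHN cohort, 821 days or 27.0 months before Amendment 5. Part of that cohort could be exposed.
- 22 JAN 2021 minus 15 months is 22 OCT 2019. Taking this as the last entry date is an inference, because the 15-month statement covers subjects still on treatment, not those in follow-up.

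**2. How large the bias could be (Monte Carlo, 400,000 subjects per scenario)**

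Let T be time on treatment (at most 24 months), D survival time, and E the months from first dose to the amendment.
- Censoring time under the rule: C = max(T + 2, E).
- Observed time: min(D, C), with a death counted if D ≤ C.
- Bias = Kaplan-Meier at 24 months minus true P(D > 24).

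Assumptions, none from the documents:
- *Exponential set:* median time on treatment 2.5 or 5 months; median survival 24 to 36 months on treatment and 6 to 12 months after stopping.
- *Mixture set:* 10%, 20% or 30% long-term treated (median 30 months before the cap), the rest with median 2.5 months; median survival after stopping 12 and 6 months respectively.
- Uniform entry in each window.

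| Entry window | Exponential: bias, points | Mixture: true → Kaplan-Meier 2-year OS, % |
|---|---|---|
| JUN 2017–JAN 2019 | 0 | 15.2→15.2; 21.3→21.3; 27.4→27.4 |
| JUN 2017–OCT 2019 | 0 to +0.4 | 15.2→15.8; 21.2→22.0; 27.3→28.3 |
| OCT 2018–OCT 2019 | −0.1 to +1.1 | 15.2→17.0; 21.2→23.6; 27.6→30.2 |
| JAN 2019–OCT 2019 | 0 to +2.3 | 15.1→18.1; 21.1→24.8; 27.4→31.4 |

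The mixture biases in the last three rows are +0.6 to +1.0, +1.8 to +2.6 and +3.0 to +4.0 points. A second set of assumptions (15% or 35% long-term treated, post-treatment median 6 or 9 months) gave:
- +0.9 to +1.7 points for entry 15–36 months before the amendment;
- +2.3 to +3.5 points for 15–27 months;
- +4.3 to +5.4 points for 15–24 months.

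**Risk-set composition at month 23.** The share on treatment or within 60 days of stopping was:
- entry JUN 2017–OCT 2019: 1–26% (exponential) and 41–65% (mixture);
- entry JAN–OCT 2019: 5–69% and 82–92%.

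**One-year OS.** No bias in any scenario, because every entry window closes 15 months before the amendment.

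**Common cutoff at the amendment date.** With vital status known at that date, the true value was recovered within 0.1 point for the 15–36 and 15–27 month windows, and within about 1 point for 15–24 months. If subjects are instead censored at their last contact before the cutoff, part of the bias remains: about 2.4 to 4 points in the 15–24 month case. Contact is 2-weekly on treatment and 12-weekly off it.

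**The case against.** A reader might infer that late risk sets keep only subjects on treatment or just off it, and that 2-year OS is therefore overstated. The documents do not support that. It would hold if the rule had applied from the first subject; true 2-year OS of 9.5% would then appear as 25.0% in one exponential scenario. In fact the rule came late, after years of 12-weekly contact, and no scenario using the real amendment date gave a month-23 risk set made up entirely of such subjects. For subjects already past their safety visits on 22 JAN 2021, the stop is simply a calendar cutoff. The problem is that on-treatment subjects are not cut off at the same time.

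The largest figures need all entry within 24 months of the amendment. That cannot describe the whole study, since Phase 1 responses were reported in 2017.

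Precision also matters. No Phase 2 cohort exceeds 57 subjects. At 23% survival, a simple binomial 95% half-width is 1.96 × √(0.23 × 0.77 / 50) = 11.7 points for n = 50, and 20.6 points for n = 16. A bias of 1 or 2 points is well inside that. OS carries no hypothesis test, and the primary endpoint, ORR, is untouched.

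Finally, SAP 7.3.8 already has a cutoff term, and Protocol 7.11.2 already allowed survival follow-up to be reduced or eliminated after the final primary analysis.

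All of this stands, and it limits the point to a conditional bias in a secondary estimate. It does not remove the mechanism: the cutoff is undated, and nothing in the SAP stops on-treatment subjects from contributing time after off-treatment subjects have left.

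**Conclusion.** The point holds in a limited form. For subjects under 24 months from first dose on 22 JAN 2021, the plan as written makes OS censoring depend on treatment status. Any resulting bias in 2-year OS is upward, provided subjects die more slowly on treatment than after it.

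Its size cannot be fixed from the documents:
- zero if all were first dosed by about JAN 2019;
- about 0 to 2 points with broad enrolment;
- about 2 to 5 points only in cohorts enrolled mostly in 2019 with a sizeable long-treated share. PD-1 refractory SCCHN is a possible example. With short times on treatment the bias is near zero even there.

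One-year OS is unaffected if, as the 15-month statement suggests, entry ended at least 12 months before the amendment. OS estimates beyond 24 months are more exposed than the 2-year figure. The hazards and entry windows are assumptions; the dates and follow-up rules are the protocol's own.

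**What to change.** Amend SAP 7.3.8 as follows:
- Set one OS data cutoff, a single calendar date for all sites, at or before the date Amendment 5 was implemented. Site-by-site ethics approval dates should not be used.
- Censor every subject alive on that date at that date, whether on or off treatment. List later deaths descriptively.
- Establish off-treatment vital status as of the cutoff from the scheduled 12-weekly contact, or from the patient and public records named in Protocol 7.11.2, where consent allows. Censor at an earlier last contact only where status cannot be established, and report how many such subjects there are.
- Report, per cohort, how many subjects had under 24 months of potential follow-up at the cutoff. This shows directly whether the issue is material.

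The cost is SAP wording plus some vital-status retrieval. A few later deaths and some late follow-up leave the estimate. In a cohort enrolled wholly within 24 months of the cutoff, nobody would have full 2-year follow-up, so its 2-year OS would have to be flagged as resting on very few subjects or not reported. The sponsor's own statement that the data were sufficient by Amendment 5 makes this a modest concession.

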6.5. End of Study

The end of the study will occur when all subjects have completed the last study follow-up visit or have discontinued study treatment and have completed applicable follow-up assessments. Additionally, subjects will be considered as having completed the study if they meet any of the following criteria:

- Subject dies and a date of death is available.
- Subject is known to have died; however, the date of death cannot be obtained.
(NOTE: Every effort must be made to obtain the date of death.)
- Consent is withdrawn for any further contact related to this study.
 - Every reasonable effort should be made to determine the reason a subject withdraws prematurely, and this information should be recorded in the eCRF.
- The study is terminated by the sponsor.
- The study is terminated by the local health authority or IRB or IEC.

6.6. Unscheduled Visits

Unscheduled study visits may occur at any time if medically warranted. Any assessments performed at those visits should be recorded in the eCRF.

7. CONDUCT OF STUDY ASSESSMENTS AND PROCEDURES

Individual study procedures are described in detail below. It may be necessary to perform these procedures at unscheduled timepoints if deemed clinically necessary by the investigator. Furthermore, additional evaluations/testing may be deemed necessary for reasons related to subject safety. In some cases, such evaluation/testing may be potentially sensitive in nature (eg, HIV, HCV), and thus local regulations may require that additional informed consent be obtained from the subject. In these cases, such evaluations/testing will be performed in accordance with those regulations. Per Section 3.1, subjects of childbearing potential must agree to take appropriate measures to avoid pregnancy in order to participate in the study ([Appendix A](#)).

7.1. Administration of Informed Consent Form

Valid informed consent must be obtained from the study subject before conducting any study-specific procedures using an ICF approved by the local IRB/IEC that contains all elements required by ICH E6 and describes the nature, scope, and possible consequences of the study in a form understandable to the study subject. Additional consent may also be required per local regulatory agencies. Local and institutional guidelines for ICF content and administration must be followed; the original signed ICF must be retained by the investigator, and a copy of the signed ICF must be provided to the study subject. The informed consent process for each subject must be documented in writing within the subject source documentation.

7.2. Interactive Response Technology System Procedure

The site will contact the IRT to obtain a subject identification number when a subject enters the prescreening phase. Upon determining that the subject is eligible for study entry, the IRT will be contacted to obtain the treatment group assignment. Additionally, the IRT will be contacted to update the subject's disposition, disease response, and for study drug resupply. Refer to the IRT manual for detailed instructions.

During Phase 2 of the study, the IRT system will be updated based on the PoS calculations discussed in Section 9.6. Probability of success calculations will be performed based on response data available within the IRT system and treatment groups may be closed to subject assignment if the PoS for a treatment group-tumor type combination is below the futility threshold. Subjects will be assigned sequentially to treatment groups that are open to assignment based on these PoS calculations. Periodically, the sponsor will review the disease response data within the IRT system for consistency with the clinical database and request changes to resolve discrepancies.

7.3. Demography and Medical History

7.3.1. Demographics and General Medical History

Demographic data and a complete medical and medication history will be collected at screening by the investigator or qualified designee and will include date of birth, race, ethnicity, medical and surgical history, and current illnesses. Medical history will include relevant medical or surgical treatment **within the last 10 years that are considered to be clinically significant** by the investigator.

7.3.2. Disease Characteristics and Treatment History

A disease-targeted medical and medication history will be collected at screening. Details regarding the subject's malignancy under study including date of diagnosis, initial and current cancer stage, tumor histology, relevant disease characteristics, and prior treatments including systemic, radiation, and surgical procedures will be recorded.

